### **Kinetics of treatment-emergent ADA response**

Number (%) of participants with treatment-emergent ADA positive response at each visit will be summarized, including titer categories (lower, moderate, and high titer), by each intervention group.

A plot of percentage of participants with treatment-emergent ADA positive response at each visit will be provided by each intervention group.

### **Association of Immunogenicity with Exposure, Safety and Efficacy**

The safety and efficacy analyses mentioned below will be conducted using the following categories:

- ADA positive participants: Participants with treatment-emergent or treatment-boosted response.
- ADA negative participants: Participants with pre-existing immunoreactivity or negative in the ADA assay at all time points.

### **Association of ADA with PK**

Associations between ADA variables (eg, ADA peak titers, neutralizing antibody status, treatment-emergent, persistent, indeterminate and transient response, treatment-boosted) and concentration of dupilumab in serum may be explored for each dupilumab dose group. A plot of

concentration of functional dupilumab versus visit will be provided by ADA classifications for the dupilumab dose group. Individual participant plots of dupilumab concentration according to ADA status will be provided to assess the impact of ADA on PK.

### **Association of ADA with clinical efficacy endpoints**

Associations between the ADA variables (eg, ADA peak titers, neutralizing antibody status, treatment-emergent, persistent and treatment-boosted) and the primary efficacy endpoint may be explored for the dupilumab dosed group.

### **Association of ADA with clinical safety endpoints**

Association of safety versus ADA status may be analyzed in the ADA population. The safety assessment may focus on the following events:

- Severe injection site reactions last longer than 24 hours or serious injection site reactions
- Hypersensitivity reactions (SMQ (20000214) hypersensitivity narrow search confirmed by medical review)
- Anaphylactic reactions (SMQ (20000021) anaphylactic reaction narrow search)

Associations between ADA variables (eg, ADA peak titers, neutralizing antibody status, treatment-emergent, persistent and treatment-boosted) and safety may be explored.

#### **4.8.3 Pharmacodynamic/genomics endpoints**

Venous blood samples will be collected at Visit 2 (Week 0), Visit 3 (Week 4), Visit 4 (Week 8), Visit 5 (Week 12), Visit 6 (Week 24), and Visit 7 (Week 36), for measurement of total serum IgE. Total IgE will be measured using validated quantitative methods.

For those participants who consent to the optional pharmacogenetic/pharmacogenomic sample collection section of the ICF, blood (serum/plasma) for possible future analysis of potential biomarkers of drug response, disease activity, safety, and the type 2 inflammation pathway, and blood samples for exploratory genetic analysis of DNA or RNA will be collected and stored for possible future use. Participation is optional. Participants who do not wish to participate in the genetic research may still participate in the study.

Total IgE will be summarized in the safety population defined as participants who actually received at least 1 dose or part of a dose of the IMP. Baseline values will be the last value collected prior to the first IMP. Descriptive statistics (including number, mean, SD, median, Q1, Q3, min, max) of biomarkers at baseline will be summarized. In addition, for participants who take the prohibited medications/procedures or rescue medications defined in [Table 5](#), the data after the medications will be censored and then last observation carried forward (LOCF) method will be implemented for missing data imputation in the analysis..

Summary plots (median with interquartile range) on values at each visit, absolute changes from baseline and percent changes from baseline will be provided for the total IgE by intervention group and visit.

Exploratory analysis of DNA, RNA and urine biomarkers will be addressed in a separate document.

#### **4.9 INTERIM ANALYSES**

No interim analysis is planned.

A primary database lock will be performed when all randomized participants in this study have completed their 24-week treatment phase. Final analyses in the CSR will be based on this database.

The database will be updated at the end of the study for all participants to include the post-treatment follow-up information and updates for the events previously ongoing at the time of the primary lock. Additional data between this database lock and last participant completing last visit will be summarized in a CSR addendum.

## 5 SUPPORTING DOCUMENTATION

### 5.1 APPENDIX 1 LIST OF ABBREVIATIONS

ADA:	anti-drug antibody
AE:	adverse event
AESIs:	adverse events of special interest
ALT:	alanine aminotransferase
ANCOVA:	analysis of covariance
AST:	aspartate aminotransferase
ATC:	anatomic category
CI:	confidence interval
CLcr:	creatinine clearance
CMH:	Cochran-Mantel-Haenszel
CMQ:	customized MedDRA query
CSR:	clinical study report
DLQI:	Dermatology Life Quality Index
DNA:	deoxyribonucleic acid
ECG:	electrocardiogram
eCRF:	electronic case report form
EMA:	European Medicines Agency
EOT:	end of treatment
EQ-5D-5L:	5-level EuroQol 5-dimensional questionnaire
FDA:	Food and Drug Administration
HADS:	hospital anxiety and depression scale
HBc Ab:	hepatitis B core antibody
HBs Ab:	hepatitis B surface antibody
HBs Ag:	hepatitis B surface antigen
HBV:	hepatitis B virus
HCV Ab:	hepatitis C virus antibodies
HLGT:	high level group term
HLT:	high level term
HRQoL:	health-related quality-of-life
IGA PN:	Investigator's global assessment for prurigo nodularis
IMP:	investigational medicinal product
ITT:	intent-to-treat
LLT:	lower-level term
LS:	least squares
MedDRA:	Medical Dictionary for Regulatory Activities
PCSA:	potentially clinically significant abnormality
PGIC:	Participant Global Impression of Change
PGIS:	Global Impression of Severity
PK:	pharmacokinetic
PN:	prurigo nodularis

PT:	preferred term
RNA:	ribonucleic acid
SAE:	serious adverse event
SAP:	statistical analysis plan
SD:	standard deviation
SDG:	standardized drug grouping
SMQ:	standardized MedDRA query
SOC:	system organ class
TEAE:	treatment-emergent adverse event
ULN:	upper limit of normal
WHO-DD:	World Health Organization-Drug Dictionary
WI-NRS:	worst-itch numeric rating scale
WOCF:	worst-observation carried forward

## 5.2 APPENDIX 2 CHANGES TO PROTOCOL-PLANNED ANALYSES

This section summarizes major statistical changes in the protocol amendment.

**Table 9 - Major statistical changes in protocol amendment(s)**

Amendment Number	Approval Date	Changes	Rationale
1	20-May-2020	To add “proportion of participants with Investigator’s Global Assessment 0 or 1 score for PN-Stage (IGA PN-S) at Week 24” as another key secondary endpoint	To include a lesion-related key secondary endpoint according to the health authority’s recommendations
		To remove the endpoint “Change from baseline in PAS total score at Week 4, Week 8, Week 12, and Week 24” in the exploratory endpoint and modify the exploratory endpoint regarding the healed lesions from PAS questionnaire analysis	To clarify the analysis on efficacy evaluation of dupilumab on skin lesions using a modified prurigo activity score (PAS) 5-item questionnaire
		To break out the secondary endpoints with multiple measuring timepoints into individual endpoints.	To clearly define the timepoints of each endpoint according to health authority’s recommendation
		To add the sensitivity analysis for secondary endpoints information, and to separate key secondary endpoints in a different row	To evaluate the robustness of the missing data imputation assumption by sensitivity analyses, and to clarify the endpoints analyses
		To add the covariate “baseline anti-depressant use (yes or no)” to primary and secondary endpoint analyses	To adjust for potential impact of anti-depressant use on the treatment effect in primary and secondary efficacy analyses
		The following wording was added: “Data collected regarding the impact of the COVID-19 or other pandemics, on the participants will be summarized (eg, discontinuation due to COVID-19). Any additional analyses and methods required to investigate the impact of COVID-19 or other pandemics requiring public health emergency on the efficacy (eg, missing data due to COVID-19) and safety will be detailed in the SAP”.	To describe alternative temporary mechanism that can be implemented in the study conduct in case of pandemic requiring public health emergency eg, COVID-19

### **5.3 APPENDIX 3 DEMOGRAPHICS AND BASELINE CHARACTERISTICS, PRIOR OR CONCOMITANT MEDICATIONS/PROCEDURES**

#### ***Demographics, baseline characteristics, medical surgical history***

The following demographics and baseline characteristics, medical and surgical history and disease characteristics at baseline will be summarized using descriptive statistics in the randomized population.

Demographic variables are

- Age in years (quantitative and qualitative variable: 18-<40, 40-<65, 65-<75, and  $\geq 75$  years),
- Gender (Male, Female),
- Race (White, Black or African American, Asian, American Indian or Alaska Native, Native Hawaiian or other Pacific Island, unknown),
- Ethnicity (Hispanic or Latino, Not Hispanic or Latino, Unknown)
- Region (Asia: Taiwan, South Korea; East Europe: Hungary; Latin America: Chile; Western Countries: USA, Canada, France, Italy, Portugal, Spain, and UK)
- Territory (North America: USA, Canada; European Union: France, Italy, Portugal, Spain, Hungary, and UK; Rest of World: Taiwan, South Korea, Chile)
- Weight in kg (quantitative and qualitative variable: (<60,  $\geq 60$ - <90,  $\geq 90$  kg)
- BMI in kg/m^2 (quantitative and qualitative variable: <25,  $\geq 25$ - <30,  $\geq 30$  kg/m^2)

Baseline safety and efficacy parameters (apart from those listed above) will be presented along with the safety and efficacy summaries.

Medical (or surgical) history includes all the relevant medical (or surgical) history during the lifetime of the participant.

This information will be coded using the version of MedDRA currently in effect at Sanofi at the time of database lock.

Comorbidity will be summarized separately. The following comorbid diseases will be summarized from electronic case report form (eCRF) pages which were filled in by investigators based on participant reporting.

- Prurigo nodularis (Yes, Ongoing condition)
- Atopic dermatitis (Yes, Ongoing condition)
- Allergic rhinitis history (Yes, Ongoing condition)
- Allergic rhinoconjunctivitis (Yes, Ongoing condition)
- Asthma history (Yes, Ongoing condition)

- Food allergy history (Yes, Ongoing condition)
- Eosinophilic esophagitis history (Yes, Ongoing condition)

### ***Disease characteristics at baseline***

The following baseline disease characteristics will be summarized by intervention group:

- Duration of PN and grouping (years; <3 and  $\geq 3$ ) to be derived as
  - (Year of randomization – Year of first diagnosis of PN) + (month of randomization – month of first diagnosis of PN)/12
- Age of onset of PN (years)
- History of atopy (atopic or non-atopic)
  - Number of mild AD participants under atopic
- Stable use of TCS/TCI (yes or no)
- Baseline WI-NRS score
- Baseline IGA PN-S score (summary and frequency by each score level)
- Baseline IGA PN-A score (summary and frequency by each score level)
- Baseline skin Pain-NRS score
- Baseline Sleep-NRS score
- Baseline PGIS score
- PAS (number of prurigo lesions in a total and in representative area, and healed prurigo lesions) at baseline
- Baseline Hospital Anxiety and Depression Scale (HADS) total score
  - Baseline Hospital Anxiety score
  - Baseline Depression Scale score
- Baseline Dermatology Life Quality Index (DLQI) score
- Baseline EuroQol five dimensions questionnaire (ED-5D-5L) (single index score and VAS)
- Frequency of alcohol drinking in the past 12 months (never, occasional, at least monthly, at least weekly, at least daily) and number of drinks on a typical day (1 or 2,  $>2$ )
- Antidepressant use (yes or no) at baseline
- HIV (positive versus negative)

### ***Prior or concomitant medications and procedure***

All medications will be coded using the World Health Organization-Drug Dictionary (WHO-DD) using the version currently in effect at Sanofi at the time of database lock.

All procedures will be coded to a PT and associated primary SOC using the version of MedDRA currently in effect at Sanofi at the time of database lock.

- Prior medications/procedures are those the participant used prior to first investigational medicinal product (IMP) injection. Prior medications/procedures can be discontinued before first administration or can be ongoing during treatment phase.
- Concomitant medications/procedures are any interventions received by the participant concomitantly to the IMP, from first administration of IMP to last IMP intake + 98 days.
- Post-treatment medications/procedures are those the participant took in the period running from the end of the concomitant medications period up to the end of the study.
- A given medication/procedure can be classified as a prior medication/procedure and/or as a concomitant medication/procedure and/or as post-treatment medication/procedure. If it cannot be determined whether a given medication/procedure was taken prior or concomitantly or post, it will be considered as prior, concomitant, and post-treatment medication/procedure.

The prior and concomitant medications/procedure will be summarized for the randomized population.

Medications will be summarized by intervention group according to the WHO-DD dictionary, considering the first digit of the anatomic category (ATC) class (anatomic category) and the first 3 digits of the ATC class (therapeutic category). All ATC codes corresponding to a medication will be summarized, and participants will be counted once in each ATC category (anatomic or therapeutic) linked to the medication. Therefore participants may be counted several time for the same medication.

The table for prior medications will be sorted by decreasing frequency of ATC followed by all other therapeutic classes based on the overall incidence across intervention groups. In case of equal frequency regarding ATCs (anatomic or therapeutic categories), alphabetical order will be used.

Concomitant medication received during first IMP to last IMP +14 days and concomitant medication received during first IMP to last IMP +98 days will be summarized separately. The tables for concomitant medications will be sorted by decreasing frequency of ATC followed by all other therapeutic classes based on the incidence in the dupilumab group. In case of equal frequency regarding ATCs (anatomic or therapeutic categories), alphabetical order will be used.

Medications will also be summarized by generic name sorted by decreasing frequency based on the incidence in the dupilumab group.

Procedures will be summarized by intervention group by primary SOC (sorted by internationally agreed order) and PT (sorted in alphabetical order), sorting is based on the overall incidence across intervention groups.

### ***Background intervention***

Participants will be required to apply moisturizers (emollients) once or twice daily for at least the 7 consecutive days immediately before baseline (Day 1) and continue until Week 36.

The compliance of moisturizers (emollients) used from 7 days before the baseline visit to Week 36 (or end of study), which is defined as the (number of days moisturizers used during the period) / (number of days within the period) x 100%, will be summarized by intervention group.

Similarly, the compliance of moisturizers (emollients) used from the baseline visit to Week 12 and Week 24 will be summarized by intervention group respectively.

In addition, the compliance of use of TCS/TCI from the baseline visit to Week 12 and Week 24 for participants with the stratification of stable use of TCS/TCI (yes) will be summarized by intervention group respectively.

### ***Prohibited medications/procedures***

The concomitant use of the following therapies is prohibited during the entire study. Study treatment will need to be discontinued in participants receiving these treatments:

- Systemic immunosuppressive/immunomodulating drugs (eg, systemic corticosteroids, cyclosporine, mycophenolate-mofetil, interferon gamma, Janus kinase inhibitors, azathioprine, methotrexate, hydroxychloroquine, dapsone, sulfasalazine, colchicine, etc)
- Other monoclonal antibodies (which are biological modifiers)
- Phototherapy, including tanning beds
- Naltrexone or other opioid antagonist
- Gabapentin, pregabalin, and thalidomide

The concomitant use of the following therapies is prohibited except if the dose has been stable for at least 3 months prior to screening, but study treatment will not need to be discontinued in participants receiving the treatments listed below. The dose should also remain stable (can be reduced or discontinued if medically indicated) and should not be increased during the study.

- Paroxetine, fluvoxamine, or other SSRIs
- SNRIs
- Amitriptyline or other tricyclic or tetracyclic antidepressants

The concomitant use of the following therapies is also prohibited during the entire study, but study treatment will not need to be discontinued in participants receiving the treatments listed below:

- Intralesional corticosteroid injections and cryotherapy

- Sedating antihistamine
- Non-sedating antihistamine if used specifically for the treatment of itch secondary to AD or PN

The number and percentage of participants who take the prohibited medications/procedures will be provided. In addition, the time (week) of first prohibited medication/procedure taken will also be analyzed using Kaplan-Meier method.

### ***Rescue medications***

The following rescue medications may be used:

- Dermatological preparations of high potency or superpotent TCS and TCI.

If medically necessary (i.e., to control intolerable PN symptoms), rescue treatment for PN may be provided to study participants at the discretion of the Investigator.

Although the use of rescue medications is allowed at any time during the study, the use of rescue medications should be delayed, if possible, for at least 14 days following the initiation of the investigational treatment. The date and time of rescue medication administration as well as the name and dosage regimen of the rescue medication must be recorded in the eCRF.

- For the purpose of the efficacy responder analysis, a pre-specified algorithm will be used to classify rescue. In addition, a blinded review of all post-baseline medications to adjudicate rescue treatment, based on medical judgment, will be performed to adjudicate rescue. Participants who receive rescue treatment as per this adjudication during the study will be considered treatment failures.

The rescue medications will be analyzed by the same method as that used for prohibited medications/procedures.

## **5.4 APPENDIX 4 DATA HANDLING CONVENTIONS**

### **Demographic formulas**

Age of onset of PN is calculated as:

$$\text{Year of PN diagnosis} - \text{Year of birth}$$

BMI is calculated as:

$$\text{Weight in kg} / (\text{height}^2 \text{ in meters})$$

## Renal function formulas

For adults, creatinine clearance (CLcr) value will be derived using the equation of Cockcroft and Gault:

$$\text{CLcr (ml/min)} = (140 - \text{age}) \times \text{weight (kg)} \times (1 - 0.15 \times \text{sex (0-M, 1-F)}) / (0.814 \times \text{creatinine} \text{ (\mu mol/l)})$$

CLcr will be calculated using the last weight measurement on or before the visit of the creatinine measurement and age at the lab sampling day. Here age is calculated as following:

$$\text{Age} = \text{age collected at screening} + \text{integer part of (lab sampling analysis day/365.25)}$$

## Analysis windows for time points

### *Efficacy assessment*

For the efficacy assessment, the reference date for the derivation of relative days of events or findings will be the randomization day. If a participant receives IMP prior to the randomization by mistake, the reference date of efficacy assessment will be the date of the first IMP administration for that participant.

For daily eDiary data (WI-NRS, skin Pain-NRS, Sleep-NRS), all available values of daily measurements will be assigned to each week window according to [Table 10](#), and then weekly average score will be calculated. Randomization day is used as the reference day (Day 1).

**Table 10 - Time window for eDiary efficacy variables**

Time	Target day	Day range for calculating weekly score
Baseline (Week 0)	1	-7- <1
Week 1	8	1-11
Week 2	15	12-18
Week 3	22	19-25
Week 4	29	26-32
Week 5	36	33-39
Week 6	43	40-46
Week 7	50	47-53
Week 8	57	54-60
Week 9	64	61-67
Week 10	71	68-74
Week 11	78	75-81

Time	Target day	Day range for calculating weekly score
Week 12	85	82-88
Week 13	92	89-95
Week 14	99	96-102
Week 15	106	103-109
Week 16	113	110-116
Week 17	120	117-123
Week 18	127	124-130
Week 19	134	131-137
Week 20	141	138-144
Week 21	148	145-151
Week 22	155	152-158
Week 23	162	159-165
Week 24	169	166-172
Week 25	176	173-179
Week 26	183	180-186
Week 27	190	187-193
Week 28	197	194-200
Week 29	204	201-207
Week 30	211	208-214
Week 31	218	215-221
Week 32	225	222-228
Week 33	232	229-235
Week 34	239	236-242
Week 35	246	243-249
Week 36	253	250-256

For other efficacy variables, all available values of scheduled measurements will be assigned to the appropriate visit window according to [Table 11](#). In the event of multiple measurements of the same test in the same window, the one closest to the targeted visit date will be used for the by-visit summary. If they are at the same number of days away from the target day, the latest one will be used.

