WI-NRS	NRS: once a day from Screening to EOS						To be recorded once a day in e-diary.	
Pain-NRS								
Sleep-NRS								
DLQI		X	X	X	X	X		Entered by participant during site visit on a tablet provided to the site.
HADS		X			X	X	X	
EQ-5D-5L		X			X	X	X	
PGIS	X	X	X	X	X	X		
PGIC			X	X	X	X		
Missed school/work days (baseline version)		X						
Missed school/work days (postbaseline version)					X	X	X	
Modified PAS (screening- baseline version)	X	X						Investigator's assessment to be entered on a tablet provided to the site.
Modified PAS (follow-up version)			X	X	X	X	X	
IGA PN-A and IGA PN-S		X	X	X	X	X	X	

- a All assessments at Visit 2 (Day 1) are to be conducted pre-IMP dose with the exception of the assessment of local tolerability of SC injections.
- b Participants who discontinue the study treatment prematurely (prior to completing the 24-week treatment period) will perform the EOT assessments at the time of discontinuation to assure a complete clinical assessment in close temporal proximity to the premature termination of study treatment. In addition, to allow assessment of participant outcomes over the stipulated study period, participants will be asked and encouraged to complete all remaining study visits and participate in all assessments according to the visit schedule.
- c In case of results showing HBs Ag (negative) and HBc Ab (positive), an HBV DNA testing will be performed and should be confirmed negative prior to randomization. In case of results showing HCV Ab (positive), HCV RNA testing will be performed and should be confirmed negative prior to randomization.
- d Assessments/procedures should be conducted in the following order: PRO, investigator assessments, safety and laboratory assessments (including sample collection for ADA, PK, biomarker, and optional DNA and RNA), and administration of IMP.
- e Refer to [Section 10.2](#) and central lab manual for collection details.
- f PK and ADA samples to be collected prior to the administration of the drug. In the event of any SAE, any AE of severe injection site reaction lasting longer than 24 hours, or any AESI of anaphylactic reaction or systemic allergic reaction that is related to IMP and require treatment, PK and ADA samples will be collected at or near the onset of the event for any additional analysis if required or for archival purposes.

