### **8.1.1 Worst-itch numeric rating scale**

Worst-itch numerical rating scale (WI-NRS) is a PRO comprised of a single item rated on a scale from 0 (“No itch”) to 10 (“Worst imaginable itch”). Participants are asked to rate the intensity of their worst pruritus (itch) over the past 24 hours using this scale.

Participants will complete the WI-NRS daily according to the SoA (see [Section 1.3](#)). The assessment tool is provided in [Section 10.7.1](#).

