## 4 STATISTICAL ANALYSES

### 4.1 GENERAL CONSIDERATIONS

In general, continuous data will be summarized using the number of observations available, mean, standard deviation (SD), median, minimum, and maximum. Categorical and ordinal data will be summarized using the count and percentage of participants.

The baseline value of efficacy parameters is defined as the last available value before randomization and prior to the first dose of study medication unless below eDiary data (WI-NRS, skin Pain-NRS and Sleep-NRS) score or otherwise specified.

The baseline for weekly average WI-NRS (skin Pain-NRS and Sleep-NRS) score is defined as the average of daily non-missing scores obtained during the 7 days prior to randomization.

The baseline value of the other parameters is defined as the last available value prior to the first dose of investigational medicinal product (IMP) if the participant is treated, or the last available value up to randomization if the participant is not exposed to IMP.

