## **4.3 PRIMARY ENDPOINT(S) ANALYSIS**

### **4.3.1 Definition of endpoint(s)**

The primary endpoint for this study is the proportion of participants with improvement (reduction) in worst-itch numeric rating scale (WI-NRS) by  $\geq 4$  from baseline to Week 12.

WI-NRS is a patient-reported outcome (PRO) comprised of a single item rated on a scale from 0 (“No itch”) to 10 (“Worst imaginable itch”). Participants are asked to rate the intensity of their worst pruritus (itch) over the past 24 hours using this scale.

The weekly average WI-NRS score at each week, which is defined as the average of daily non-missing scores within the week window of each week (see [Section 5.4](#)), will be used for analyses.

For efficacy analysis, [Table 5](#) presents the prohibited and rescue medications/procedures which will be considered as intercurrent events if the last column indicates as “Yes” and therefore be handled in the estimands for endpoints defined in [Table 3](#).

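### The Week 1 diary score counts the randomization-day entry, which is essentially pre-dose, as post-baseline data

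*SAP*

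**What the plan says.** SAP Section 5.4 (Efficacy assessment) makes the randomization day Day 1 for diary data and states that "all available values of daily measurements will be assigned to each week window". Table 10 then gives Week 1 a target of Day 8 and, in the column headed "Day range for calculating weekly score", a range of Days 1-11. Weeks 2 to 36 are all seven-day windows of target day ±3 (Week 2 is Days 12-18).

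SAP Section 4.1 defines the diary baseline as the "average of daily non-missing scores obtained during the 7 days prior to randomization", and Table 10 ends the baseline range before Day 1. The weekly score in SAP Section 4.3.1 is the mean of the non-missing daily scores in the window, with no minimum number of entries.

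On timing, footnote a of the Schedule of Activities says "All assessments at Visit 2 (Day 1) are to be conducted pre-IMP dose", apart from injection-site tolerability. Footnote d puts patient-reported outcomes first and the injection last. Protocol Section 8.1.1 describes the itch item: "Participants are asked to rate the intensity of their worst pruritus (itch) over the past 24 hours". Protocol Section 8.1.5 gives skin pain the same recall and ties sleep to the night just past.

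The note to SAP Table 11 divides Day 1 into values before (1-) and after (1+) randomization or first dose. Table 10 has no such division.

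**The concern.** A score that describes the participant before treatment should not be averaged into a post-baseline value. Here the Day 1 entry falls outside baseline and has nowhere to go but Week 1. Any treatment difference in the Week 1 mean is diluted by a day on which none can yet exist.

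Week 1 is not a named time point for any endpoint, but the score is used in several places:

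- the itch endpoints described as over time until Week 24;
- time to first reduction of at least 4 points (SAP Section 4.4.2);
- the footnotes to SAP Table 2 that allow an onset claim at the earliest qualifying week;
- the multiple-imputation model in SAP Section 5.5, which starts at `chg1winrs`;
- the set of post-baseline values from which the worst is carried forward.

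**Working it through.** **Inputs.** Week 1 window, Days 1-11: SAP Table 10. Baseline, the 7 days before Day 1: SAP Section 4.1 and Table 10. Weekly score, an unweighted mean of non-missing days: SAP Section 4.3.1. Recall periods: Protocol Sections 8.1.1 and 8.1.5.

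**1. Is Day 1 in Week 1?** Baseline covers Days -7 to <1 and Week 1 covers Days 1 to 11, so yes. Of the 36 post-baseline rows, 35 equal target ±3. Week 1 is the exception (target 8, -7/+3).

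**2. Is the Day 1 entry pre-dose?** For sleep, yes: it concerns the night before the visit. For itch and pain it is an inference, because no clock time is fixed for the diary. An entry made before the visit procedures is wholly pre-dose. A later entry on Day 1 still looks back over pre-dose hours. Because the item asks for the worst itch in 24 hours, the answer cannot properly be lower than the worst itch in those hours.

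**3. Weight of Day 1.** With k non-missing entries in the window, one of them Day 1, the weight is 1/k:

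| Entries k | Weight of Day 1 |
|---|---|
| 11 (complete) | 1/11 = 9.1% |
| 7 | 1/7 = 14.3% |
| 4 | 1/4 = 25% |
| 1 (Day 1 only) | 100% |

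Protocol criterion I 03 requires at least 4 of 7 scores for baseline. No such rule is stated after baseline, so the last row is possible.

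**4. Effect on the Week 1 treatment difference.** If the Day 1 score is pre-dose, randomization makes its expected between-arm difference zero. With complete diaries and mean difference D over Days 2-11:

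Week 1 difference = (0 + 10 × D)/11 = 0.909 × D, a loss of 9.1%.

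This holds for any onset curve. Under linear onset the Days 1-11 and Days 2-11 means are 5.0 and 5.5 (ratio 0.909). Under exponential onset with a 7-day half-life they are 0.360 and 0.396 (ratio 0.909).

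**5. Effect on a Week 1 responder.** If the Day 1 score equals the participant's baseline mean (assumption), a Week 1 reduction of 4 requires (0 + 10 × m)/11 ≥ 4, so m ≥ 4.4 over Days 2-11. The threshold is slightly stricter than stated, equally in both arms.

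**6. What does not move.** The main analyses of the primary and key secondary endpoints use Week 12 or Week 24, with non-responder imputation for missing data and for prohibited or rescue medication. Week 1 does not enter. Week 24 percent change in itch, and Week 24 pain and sleep, are in the testing hierarchy and use the hybrid imputation. Week 1 can reach them only through participants with imputed values. The documents give no basis for sizing that.

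**The case against.** The best defence is that a wide first window follows from the rule that every daily value goes into a window: Days 1-4 have no other home. Table 11 does the same on a larger scale, with a first post-baseline window of 1+ to Day 42 for a target of Day 29. This stands as a defence of Days 2-4, which are genuine post-dose data. It does not cover Day 1, which is exactly where Table 11 draws a line.

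A reader might infer that the whole 11-day window is an error and that Days 5-11 is the correct one. Under assumed exponential onset with time constants of 7, 14 and 28 days, Days 1-11 show 74%, 73% and 72% of the Days 5-11 effect, which suggests a dilution of 26-28%. The documents do not support that reading. They give no daily onset profile, and other curves put the loss anywhere from about 9% (full effect from Day 2) to 29% (linear). Most of it under gradual onset comes from Days 2-4: with linear onset, Days 2-11 already give 5.5/7.0 = 79% of the Days 5-11 effect, against 5.0/7.0 = 71% with Day 1 included. Averaging Days 2-4 measures a slightly earlier period; it is not a bias.

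Three further inferences fail. No Week 1 pain or sleep endpoint is planned; the named weeks are 4, 8, 12 and 24. Nothing shows how often Week 1 would be the worst value carried forward, a rule confined to users of prohibited or rescue medication and to missing data after discontinuation for lack of efficacy. And the window is the same in both arms, so it makes a Week 1 onset claim harder and does not favour dupilumab. The onset endpoint is also worded on daily scores; analysed that way, Table 10 does not affect it.

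**Conclusion.** The point holds in a narrow form. Table 10 classes an essentially pre-dose diary score as post-baseline, inconsistently with Table 11. With complete diaries it carries 1/11 of the Week 1 mean and removes about 9% of the Week 1 treatment difference relative to Days 2-11. With sparse diaries its share is larger, up to the whole score for someone whose only entry in the window is on Day 1. In that case the Week 1 value is entirely pre-treatment, yet it prevents the participant from counting as having no post-baseline data, the condition under which SAP Section 4.4.2 substitutes baseline.

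The 9% rests on complete diaries and on the Day 1 entry being pre-dose, which is certain for sleep and inferred for itch and pain. The effect is confined to supportive itch analyses and the imputation inputs. It is a minor correction, worth making because it costs almost nothing.

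**What to change.** In SAP Table 10, change the Week 1 range from Days 1-11 to Days 2-11. Alternatively, carry Table 11's 1+ rule into Table 10 so that only Day 1 entries made after the first dose count. The Day 2 start is simpler: it needs no diary entry times, and a post-dose entry on Day 1 would still recall pre-dose hours. Add a clause in SAP Section 5.4 saying that the Day 1 diary score belongs to no weekly window, since the text there assigns all daily values to one.

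The cost is one diary day fewer in the Week 1 mean. A participant whose only post-baseline entry is on Day 1 would then be treated as having none, which is the accurate description.

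Narrowing further to Days 5-11 is optional. It would match the other weeks, but it needs a stated rule for Days 2-4 and would set aside real post-dose data. If Days 2-11 is kept, one sentence giving the reason for the longer first window is enough.
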